[figure not shown]

## 1.0 BACKGROUND AND RATIONALE

The transition from active treatment to survivorship is one of the most challenging periods for ovarian cancer survivors. After completing intensive surgery and chemotherapy, survivors often transition to a surveillance period without further treatment and limited contact with their oncology team. Many survivors struggle to reintegrate into their “normal” lives, and experience high rates of physical and emotional distress, fatigue, anxiety, and unmet needs due to disease- and treatment-related sequelae.

Exercise has been shown to improve quality of life (QOL), fatigue, and mood, while reducing the risk of disease recurrence and cancer-related mortality in several cancers. In ovarian cancer, observational studies have documented associations between exercise and improved QOL, but studies have been limited by a reliance upon participants’ retrospective recall of activity levels and an inability to examine causality. Only 20% of survivors meet national guidelines for recommended levels of physical activity and 40% report a drop in exercise in the year after diagnosis. Ovarian cancer survivors report an interest in participating in home-based, walking programs to increase physical activity. To date, however, few randomized trials have tested exercise interventions in ovarian cancer. We recently completed a pilot study of wearable accelerometers in ovarian cancer patients at Dana-Farber Cancer Institute (DFCI). Although increasing physical activity was not a primary endpoint, participants were enthusiastic about using wearable devices and spontaneously increased their step counts over a 3-week period (3520 vs. 4374). These findings suggest that smartphone-based interventions coupled with wearable devices may offer a low-cost, scalable strategy to increase physical activity in patients with ovarian cancer.

Smartphone-based health interventions have demonstrated efficacy in achieving sustained behavior change in contexts ranging from smoking cessation to physical activity, particularly when combined with insights from behavioral economics. Recently, [name] et al. (co-I) randomized healthy participants to a control group or a mobile health intervention that combined gamification (e.g., the use of non-financial micro-incentives like points, levels, and badges) and social incentives (e.g., collaboration, accountability, and peer support) to increase physical activity. During the 3-month study, participants in the intervention arm achieved physical activity goals at significantly greater rates (53% vs. 32%;  $P < 0.001$ ) compared with controls, and averaged nearly 1000 steps more per day ( $P < 0.001$ ). Differences persisted during the 3-month follow-up period after the intervention ended (44% vs. 33%;  $P < 0.001$ ), suggesting that the behavior change may have been sustained through the strengthening of existing social networks. It is unclear whether this strategy can be successfully applied in less healthy populations, including cancer patients, to increase physical activity.

We propose a study to evaluate the efficacy of a social support-based gamification intervention vs. control to increase physical activity in ovarian cancer survivors. Prior to launching a full-scale RCT, we propose a 20-ovarian cancer survivor + partner run-in phase of the social support-based gamification intervention to ensure the interventions’ feasibility, acceptability, and preliminary effectiveness. Participants in the social support-based gamification intervention will choose a partner (family/friend) with whom to set collaborative physical activity goals and receive automated feedback through an NIH-funded software platform called Way to Health. All participants, including partners, will use wearable devices to passively collect physical activity data. After completion of the 20 patient + partner run-in phase, we will test the efficacy of the social support-based gamification intervention vs. control in 148 ovarian cancer survivors’ daily steps (primary outcome) and QOL, anxiety, and health care utilization (secondary outcomes) at baseline, 14 and 26 weeks.

## **2.0 OBJECTIVES**

### Preliminary Analysis (20 ovarian cancer survivors + partners run-in)

Objective: To assess the feasibility and acceptability of a gamification intervention designed to leverage social incentives and a wearable accelerometer in 20 survivors + partners.

- Hypotheses: It will be feasible to recruit and retain participants and to deliver the intervention.
- Hypothesis: Participants will perceive the intervention as acceptable, and effective in increasing their activity levels.

### Final Analysis (RCT with 148 ovarian cancer survivors and 74 partners)

Objective: To evaluate the effectiveness of a modified game-based intervention designed to enhance social incentives in increasing physical activity relative to control.

- Hypothesis: The game-based intervention will increase physical activity at 14 weeks compared with a wearable device.
- Hypothesis: The relative differences in activity between groups will persist at 26 weeks.

Objective: To evaluate the effectiveness of a game-based intervention designed to enhance social incentives in improving ovarian cancer survivors' quality of life and mental health relative to control.

- Hypothesis: Participants in the game-based intervention arm will report significantly better quality of life and lower rates of anxiety or depression at 14 and 26 weeks, compared to those with a wearable device.

A preliminary analysis will be conducted after the 20-patient run-in of the intervention. The final analysis will take place after all patients have completed the study. The final analysis will exclude patients from the run-in phase, since this group of patients will not undergo randomization.

## **3.0 RESEARCH SUBJECT SELECTION**

### **3.1 Eligibility Criteria**

Patients will be eligible if they have newly diagnosed ovarian cancer and are  $\leq 3$  months of completing chemotherapy, read English, and do not have cognitive or visual impairments that would preclude participation.

### **3.2 Exclusion Criteria**

Patients will be excluded if they are already participating in an mHealth intervention, are unable to ambulate, do not have a smartphone to transmit data from the wearable tracker, or are unable to select a partner with a smartphone to transmit data from the wearable tracker.

## **4.0 RESEARCH SUBJECT ENTRY**

## 4.1 Subject Recruitment and Enrollment

### 4.11 Screening & Recruitment

Prior to obtaining informed consent, study staff will review the electronic medical records of patients who may meet eligibility criteria. These patients' medical records will only be reviewed to confirm this protected health information (PHI), and it will only be shared with providers in the context of patients' eligibility for the study.

When an eligible patient is identified, study staff will contact the patient's oncology provider to confirm she meets the eligibility criteria and to request permission to approach the patient to introduce the study. If the oncology provider deems the patient ineligible or too distressed to participate in a clinical study at this time, the patient will not be approached for inclusion.

PHI will not be shared with anyone outside of the study team and patients' oncology providers. All emails will be sent within the Partners firewall; emails containing PHI that are sent outside the Partners firewall will be sent via the HIPAA-compliant "send secure." A HIPAA waiver requesting permission to review the PHI of these select, potentially eligible patients prior to consent during screening and recruitment has been submitted to justify this process.

If the patient is approved to approach for enrollment, the research assistant (RA) will coordinate with the oncology provider to meet with the patient to discuss the study at the time of her clinic visit.

### 4.12 Informed Consent

If a patient agrees to learn more about the study, the RA will describe the study, review the consent form, answer any questions, and provide her contact information. The RA will encourage patients to take their time in deciding whether they want to participate in the study or not.

If a patient is interested in participating, the RA will obtain informed consent within the Way to Health platform, as in several other IRB-approved studies throughout the United States (e.g. University of Pennsylvania, Framingham Cohort), in order to ensure that they are properly informed about the data being collected from the accelerometers and by the platform. The partners of patients will also provide in-app consent via Way to Health. The text of the in-app informed consent is included as the single informed consent form for this study.

If a patient is unsure if she would like to participate in the study, they will be offered the consent form to review and the contact information of study staff. If no contact is made after a few days, the RA will contact the patient. If the patient decides to participate, the patient will enter the informed consent process along with a partner of their choosing. If a patient is not interested, the RA will thank her for considering, reassure the patient that the process will have no impact on her care. No further interactions will occur with patients who either decline or prove ineligible for the study. Patients will not be contacted after three unreturned voicemails.

## 4.2 Subject Registration and Randomization

A member of the study team will register eligible patients enrolled at Dana-Farber in the Clinical Trials Management System (CTMS) OnCore. In order to minimize workflow disruptions for this social/behavioral protocol because the intervention will typically begin immediately after informed consent, registrations will occur retrospectively (as per DF/HCC SOP REGIST-101a) within 10 days of study enrollment if possible. An

investigator will confirm eligibility criteria and a member of the study team will complete the protocol-specific eligibility checklist.

As in the other supportive care interventional trial currently underway in our research group (DF/HCC Protocol 16-477), the study team will register and randomize applicable patients, rather than ODQ doing so, because the intervention will typically begin immediately after informed consent. Randomization will be performed using a 1:1 ratio using a computer-generated random allocation sequence with blocks of 4 in order to maintain balance between study arms over time. Please refer to the protocol schema for details.

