### 5.32 Way to Health Platform

The Way to Health platform is an automated information technology platform developed at the University of Pennsylvania that integrates wireless devices, clinical trial randomization and enrollment processes, messaging (text, e-mail or voice), self-administered surveys, automatic transfers of financial incentives, and secure data capture for research purposes. Way to Health has been used with patients in IRB-approved protocols in prior behavioral intervention studies. The Way to Health platform will be used in both the control arm and interventional arm of our studies. In the control arm, patients will receive access to the Way to Health platform in order for the study team to receive their accelerometer data, and to process payments – however, none of the gamification features of the platform will be turned on for patients in the control arm. In the intervention arm, patients and their partners will have access to the Way to Health platform in order for the study team to receive their accelerometer data and to process payments. Patients and their partners in the intervention arm will also have access to the gamification features of the Way to Health platform, as described in section 5.34.

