### 5.34 Intervention

On Day 0, patients receiving the intervention will be given two wearable accelerometers, and the study's research assistant will explain to them how to use the devices. Participants will select a family member or friend to enhance social incentives by motivating the individual towards her goal by participating in the intervention with them, so the patient will be asked to give the second fitness to a partner with whom she will participate in the study. After recording their steps passively for 2 weeks, patients will be asked to set a step goal to increase with their partner. The step goal should be of 33% to 50% higher than baseline or to choose their own goal (minimum  $\geq 1500$  steps greater than baseline). Ovarian cancer survivors and their partners will sign a pre-commitment contract agreeing to try their best to achieve their daily step goal, which helps to motivate behavior change. Participants will also receive an exercise prescription (Appendix E) which has been recommended in the care of midlife and older women and aims to motivate exercise behavior change.

At the start of each week, participants receive 70 points (10 for each day). Points are endowed to leverage loss aversion – a concept from prospect theory that reveals that individuals are more motivated by losses than gains. Each day participants are informed of their step count. If the step goal was achieved, they keep the points. However, each day the goal is not met, they are informed that they lost 10 points. Points are replenished at the start of the week to leverage the “fresh start effect.” Participants will be offered the opportunity to move up or down “levels” within the platform. At the end of the week, if the participant has  $\geq 40$  points, she will advance up one level. Levels include: blue (lowest), bronze, silver, gold, platinum (highest). If she has  $< 40$  points, she will drop down one level. This creates a sense of achievable goals (goal gradients) and longer-term loss aversion.

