### *Final Analysis*

148 patients will be randomized 1:1 to one of the two arms – accelerometer only, or accelerometer + gamification + social support. For the outcome of change in steps, we will compare the change in daily steps from baseline to the 14-week T1 time point between the intervention arm and control arm to conclude that the intervention is promising for further study. We use 1000 steps as our threshold for powering statistical significance, which for the average person is about half a mile. A priori power calculations assumed a baseline mean step count of 6000 steps in the control group with a standard deviation of 2000 steps, a 15% dropout rate, and a 2-sided  $\alpha$  of 0.05. It was estimated that a sample of 148 participants (74 per arm) would ensure 80% power to detect a 1000 step difference between the gamification + social support and control arms in the change in mean daily steps from baseline to the maintenance phase.

Fitness tracker	Gamification / social support	Arm	Sample size
+	-	1 (Accelerometer only)	74
+	+	2 (Accelerometer + gamification + social support)	74
		Total	148

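### A single fixed block size of 4, named in the protocol and used by the team that also recruits, could let staff know about one third of allocations in advance

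*Combined protocol and SAP*

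**What the plan says.** Section 4.2 sets allocation by a "computer-generated random allocation sequence with blocks of 4", in a 1:1 ratio, to keep the arms balanced as recruitment proceeds. No second block size and no stratification factor appears there or in section 6.2, where "148 patients will be randomized 1:1 to one of the two arms". Section 4.2 refers the reader to the protocol schema for more detail; that figure is not shown in the text available.

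On who does what:

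- **Screening and approach (4.11).** Study staff screen the medical records. The oncology provider confirms eligibility and may rule a patient out as too distressed at that time. The research assistant then meets the patient at a clinic visit.
- **Consent (4.12).** "the RA will obtain informed consent within the Way to Health platform".
- **Randomisation (4.2).** "the study team will register and randomize applicable patients, rather than ODQ doing so". The reason given is that the intervention usually starts straight after consent.
- **Delivery (5.33 and 5.34).** On Day 0 a control patient receives one device, whereas "patients receiving the intervention will be given two wearable accelerometers". The research assistant explains the devices in both arms.

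Section 5.32 says in general terms that the platform "integrates wireless devices, clinical trial randomization and enrollment processes". The text does not say that the platform holds or conceals this trial's sequence, and it names no sequence holder or independent randomiser.

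**The concern.** In a two-arm permuted block of known fixed size, the last allocation is settled by those before it, and sometimes the last two are. To use this, a recruiter does not need the future list. She needs the block size, which the protocol states, the order of past allocations, which the device hand-out reveals, and the point at which each block starts, which follows from counting in fours along a single unstratified sequence.

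If the next arm is known or likely, judgement about whether and when to approach a patient can be coloured by it, even without intent. Patients who seem more motivated could then drift towards one arm. The between-arm comparison of change in steps, and the self-reported secondary outcomes, would then reflect who was recruited as well as what was delivered. The arms cannot be masked, so concealing the next allocation is the main protection at entry.

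**Working it through.** **Inputs.** Block size 4, ratio 1:1 and a study-team randomiser (4.2); 148 patients (6.2); arm visible on Day 0 (5.33, 5.34). The plan gives no figure for predictability, so there is none to reproduce. Its sample size is not in question: with SD 2000, difference 1000, two-sided 5% and 80% power, n = 62.8 per arm, and 62.8 / 0.85 = 73.9, which agrees with the stated 74.

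**Certain allocations, fixed blocks of 4.** There are 6 orderings of two A and two B.

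- AABB and BBAA leave the last two places certain.
- The other four orderings leave only the last place certain.
- Mean per block = (2 × 2 + 4 × 1) / 6 = 4/3 of 4 places = 33.3%. In any one block the share is 25% or 50%.
- 148 / 4 = 37 complete blocks, and 37 × 4/3 = 49.3 certain allocations. The 95% range over possible sequences is 44 to 55.

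**Best guess, fixed blocks of 4.** The rule is to guess the arm that is behind within the block and toss a coin when the arms are level.

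- Place 1: 1/2.
- Place 2: 2/3.
- Place 3: 1/3 × 1 + 2/3 × 1/2 = 2/3.
- Place 4: 1.
- Mean = (0.500 + 0.667 + 0.667 + 1.000) / 4 = 70.8%, or about 105 of 148 against 74 by chance.

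**Alternatives.** Fixed sizes were enumerated exactly. Mixed sizes were simulated (1,000 trials of 148 patients), for a guesser who knows the set of sizes and all past allocations but not the current block size.

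| Scheme | Certain | Best guess correct |
|---|---|---|
| Fixed 4 (the plan) | 33.3% | 70.8% |
| Fixed 6 | 25.0% | 68.3% |
| Fixed 8 | 20.0% | 66.6% |
| Random 4, 6 | about 5.4% | about 69.2% |
| Random 4, 6, 8 | about 2.3% | about 68.0% |

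With random 4, 6 and 8, the certain allocations number about 0.023 × 148 = 3.4, compared with 49.3. A larger fixed block does much less for certainty. Varying the size removes nearly all sure foreknowledge but moves best-guess accuracy by under 3 percentage points.

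**The case against.** The strongest reply is that recruiters have little room to act on a prediction. Section 5.1 describes the randomised patients as consecutive, the provider must agree before any approach, the meeting is tied to a clinic visit, and patients may take their time and must bring a partner of their own choosing. Matching a chosen patient to a predicted place is therefore hard. This stands as a limit on the risk. It does not remove it: the provider's view of distress is a judgement, eligibility runs for up to three months after chemotherapy (3.1), and the timing of approach and follow-up rests partly with staff.

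The platform may already hold the sequence, and the missing schema may say more. Both are possible. A hidden list would still not stop deduction from past arms with a published fixed block size.

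A reader might go further and put the bias in steps. If every best guess were exploited by choosing patients whose expected change is d higher or lower, the bias would be 2 × (2 × 0.708 − 1) × d = 0.83d. The documents give no value for d. Recruiters see no step data before Day 0, and a fitter patient need not show a larger change. On the same formula, mixed blocks would still leave 2 × (2 × 0.68 − 1) × d = 0.72d. So this calculation supports neither a stated bias nor a claim that varying the blocks cures it.

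A reader might also infer that no analysis could help. That is too absolute. The six-minute walk, performance status, HADS and activity questions could support adjustment for measured differences where they are collected before allocation, though not for unmeasured motivation.

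**Conclusion.** The point holds as a weakness in allocation concealment that is cheap to mend. Under the text as written, staff who track allocations could know on average 33% of them (about 49 of 148) before consent, and could guess 71%. This assumes one unstratified sequence, knowledge of the block size and block starts, and a complete view of past arms; the visible text makes each of these plausible. It shows exposure only: nothing in the documents indicates that allocations have been predicted or patients steered. The size of any resulting bias is not derivable, and the planned sample size is unaffected. The absence of strata and of a concealment procedure is a statement about the visible text, since the schema is not shown.

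**What to change.** In section 4.2, replace the reference to blocks of 4 with randomly varying permuted blocks (for example 4, 6 and 8), and record the sizes in a separate document that recruiting staff do not hold. State that the Way to Health platform holds the sequence and releases each allocation only after eligibility is confirmed and consent is recorded, and after the baseline interview when that is done on Day 0. Release should not wait for the interview in every case: section 5.51 allows it at a later visit or remotely, and section 4.2 expects the intervention to begin soon after consent.

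The cost is a short edit to 4.2, a new computer-generated list and set-up on a platform already in the trial. Day 0 workflow changes slightly, because the eligibility check must be complete before release. The two arms could differ by at most 4 patients at the end, if the last block of 8 is cut off halfway; 37 full blocks of 4 would give none. The change removes sure foreknowledge but not all predictability, so the varying sizes and the controlled release should be adopted together.

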## 5.0 STUDY DESIGN AND METHODS

### 5.1 Design/Study Type

We will enroll twenty ovarian cancer survivors and their partners (i.e. family member or friend) in a single-arm run-in of the accelerometer + gamification + social support intervention. Next, 148 consecutive patients who meet inclusion criteria will be randomized to one of two arms: accelerometer only (arm 1), or accelerometer + gamification + social support (arm 2).

After the first twenty patients complete the intervention, we will conduct a preliminary analysis (n=20) to assess our aims of feasibility, acceptability, and perceived effectiveness.

After all patients complete the study requirements, we will assess effectiveness outcomes of physical activity, quality of life and mental health for patients randomized to the control arm and intervention arm of the study (n=148). We will exclude patients from the run-in phase from the final analysis since these patients will not undergo randomization. Our final analyses will provide preliminary estimates of feasibility, acceptability, safety outcomes, scale scores, missing data, and participant and physician feedback.

